Appendix D Actions Required in Cases of Increases in Liver Biochemistry and Evaluation of Hy's Law

1. Introduction

This Appendix describes the process to be followed in order to identify and appropriately report cases of Hy's Law (HL). It is not intended to be a comprehensive guide to the management of elevated liver biochemistries.

During the course of the study the Investigator will remain vigilant for increases in liver biochemistry. The Investigator is responsible for determining whether a patient meets potential Hy's Law (PHL) criteria at any point during the study.

The Investigator participates, together with AstraZeneca clinical project representatives, in review and assessment of cases meeting PHL criteria to agree whether HL criteria are met. HL criteria are met if there is no alternative explanation for the elevations in liver biochemistry other than Drug Induced Liver Injury (DILI) caused by the Investigational Product (IP).

The Investigator is responsible for recording data pertaining to PHL/HL cases and for reporting Adverse Events (AE) and Serious Adverse Events (SAE) according to the outcome of the review and assessment in line with standard safety reporting processes.

2. Definitions

Potential Hy's Law

Aspartate Aminotransferase (AST) or Alanine Aminotransferase (ALT) $\geq 3 \times$ Upper Limit of Normal (ULN) **together with** Total Bilirubin (TBL) $\geq 2 \times$ ULN at any point during the study following the start of study medication irrespective of an increase in Alkaline Phosphatase (ALP).

A Potential Hy's Law (PHL) case is defined as a study patient with an increase in serum AST or ALT $\geq 3 \times$ ULN together with total bilirubin (TBL) $\geq 2 \times$ ULN irrespective of serum ALP, at any point during the study following the start of study medication.

Hy's Law

AST or ALT $\geq 3 \times$ ULN **together with** TBL $\geq 2 \times$ ULN, where no other reason, other than the IP, can be found to explain the combination of increases, eg, elevated ALP indicating cholestasis, viral hepatitis, another drug.

For PHL and HL the elevation in transaminases must precede or be coincident with (ie, on the same day) the elevation in TBL, but there is no specified timeframe within which the elevations in transaminases and TBL must occur.

A HL case is defined as a study patient with an increase in serum AST or ALT $\geq 3 \times$ ULN together with TBL $\geq 2 \times$ ULN, where no other reason can be found to explain the combination of increases, eg, elevated serum ALP indicating cholestasis, viral hepatitis,

another drug. For PHL and HL to be met the elevation in transaminases must precede or be coincident with (ie, on the same day) the elevation in TBL, but there is no specified timeframe within which the elevations in transaminases and TBL must occur.

3. Identification of Potential Hy's Law Cases

In order to identify cases of PHL it is important to perform a comprehensive review of laboratory data for any patient who meets any of the following identification criteria in isolation or in combination:

- ALT $\geq 3 \times \text{ULN}$
- AST $\geq 3 \times \text{ULN}$
- TBL $\geq 2 \times \text{ULN}$

When a patient meets any of the identification criteria, in isolation or in combination, the central laboratory will immediately send an alert to the Investigator (also sent to AstraZeneca representative).

The Investigator will also remain vigilant for any local laboratory reports where the identification criteria are met, where this is the case the Investigator will:

- Notify the AstraZeneca representative
- Request a repeat of the test (new blood draw) by the central laboratory
- Complete the appropriate unscheduled laboratory CRF module(s) with the original local laboratory test result.

When the identification criteria are met from central or local laboratory results the Investigator will without delay:

- Determine whether the patient meets PHL criteria (see Section 2. Definitions within this Appendix for definition) by reviewing laboratory reports from all previous visits (including both central and local laboratory results).

The Investigator will without delay review each new laboratory report and if the identification criteria are met will:

- Notify the AstraZeneca representative
- Determine whether the patient meets PHL criteria (see Section 2. Definitions within this Appendix for definition) by reviewing laboratory reports from all previous visits
- Promptly enter the laboratory data into the laboratory CRF.

4. Follow-up

4.1 Potential Hy's Law Criteria not met

If the patient does not meet PHL criteria the Investigator will:

- Perform follow-up on subsequent laboratory results according to the guidance provided in the CSP.

4.2 Potential Hy's Law Criteria met

If the patient does meet PHL criteria the Investigator will:

- Determine whether PHL criteria were met at any study visit prior to starting study treatment (see Section 6. Actions Required when Potential Hy's Law Criteria are Met Before and After Starting Study Treatment).
- Notify the AstraZeneca representative who will then inform the central study team.

The Study Physician contacts the Investigator, to provide guidance, discuss and agree an approach for the study patients' follow-up and the continuous review of data. Subsequent to this contact the Investigator will:

- Monitor the patient until liver biochemistry parameters and appropriate clinical symptoms and signs return to normal or baseline levels, or as long as medically indicated.
- Investigate the etiology of the event and perform diagnostic investigations as discussed with the Study Physician. For studies using a central laboratory add: This includes deciding which the tests available in the HL lab kit should be used.
- Complete the 3 Liver CRF Modules as information becomes available
- If at any time (in consultation with the Study Physician) the PHL case meets serious criteria, report it as an SAE using standard reporting procedures.

5. Review and Assessment of Potential Hy's Law Cases

The instructions in this Section should be followed for all cases where PHL criteria are met.

No later than 3 weeks after the biochemistry abnormality was initially detected, the Study Physician contacts the Investigator in order to review available data and agree on whether there is an alternative explanation for meeting PHL criteria other than DILI caused by the IP. The AstraZeneca Global Clinical Lead or equivalent and Global Safety Physician will also be involved in this review together with other patient matter experts as appropriate.

According to the outcome of the review and assessment, the Investigator will follow the instructions below.

If there is an agreed alternative explanation for the ALT or AST and TBL elevations, a determination of whether the alternative explanation is an AE will be made and subsequently whether the AE meets the criteria for a SAE:

- If the alternative explanation is **not** an AE, record the alternative explanation on the appropriate CRF.
- If the alternative explanation is an AE/SAE, record the AE /SAE in the CRF accordingly and follow the AZ standard processes.

If it is agreed that there is **no** explanation that would explain the ALT or AST and TBL elevations other than the IP:

- Report an SAE (report term ‘HL’) according to AstraZeneca standard processes.
 - The ‘Medically Important’ serious criterion should be used if no other serious criteria apply
 - As there is no alternative explanation for the HL case, a causality assessment of ‘related’ should be assigned.

If, there is an unavoidable delay, of over 3 weeks, in obtaining the information necessary to assess whether or not the case meets the criteria for HL, then it is assumed that there is no alternative explanation until such time as an informed decision can be made:

- Report an SAE (report term ‘PHL’) applying serious criteria and causality assessment as per above.
- Continue follow-up and review according to agreed plan. Once the necessary supplementary information is obtained, repeat the review and assessment to determine whether HL criteria are met. Update the SAE report according to the outcome of the review amending the reported term if an alternative explanation for the liver biochemistry elevations is determined.

6. Actions Required when Potential Hy’s Law Criteria are Met Before and After Starting Study Treatment

This section is applicable to patients with liver metastases who meet PHL criteria on study treatment having previously met PHL criteria at a study visit prior to starting study treatment.

At the first on study treatment occurrence of PHL criteria being met the Investigator will:

- Determine if there has been a significant change in the patients’ condition[#] compared with the last visit where PHL criteria were met[#]
 - If there is no significant change no action is required
 - If there is a significant change notify the AstraZeneca representative, who will inform the central study team, then follow the subsequent process described in Section 4.2 Potential Hy’s Law Criteria met of this Appendix.

[#] A ‘significant’ change in the patient’s condition refers to a clinically relevant change in any of the individual liver biochemistry parameters (ALT, AST or total bilirubin) in isolation or in combination, or a clinically relevant change in associated symptoms. The determination of whether there has been a significant change will be at the discretion of the Investigator, this may be in consultation with the Study Physician if there is any uncertainty.

7. Actions Required for Repeat Episodes of Potential Hy’s Law

This section is applicable when a patient meets PHL criteria on study treatment and has already met PHL criteria at a previous on study treatment visit.

The requirement to conduct follow-up, review and assessment of a repeat occurrence(s) of PHL is based on the nature of the alternative cause identified for the previous occurrence.

The Investigator should determine the cause for the previous occurrence of PHL criteria being met and answer the following question:

- Was the alternative cause for the previous occurrence of PHL criteria being met found to be the disease under study eg, chronic or progressing malignant disease, severe infection or liver disease, or did the patient meet PHL criteria prior to starting study treatment and at their first on study treatment visit as described in Section 6. Actions Required when Potential Hy’s Law Criteria are Met Before and After Starting Study Treatment?

If No: follow the process described in Section 4.2 Potential Hy’s Law Criteria met of this Appendix

If Yes:

Determine if there has been a significant change in the patient’s condition[#] compared with when PHL criteria were previously met

- If there is no significant change no action is required.
- If there is a significant change follow the process described in Section 4.2 of this Appendix.

[#] A ‘significant’ change in the patient’s condition refers to a clinically relevant change in any of the individual liver biochemistry parameters (ALT, AST or total bilirubin) in isolation or in combination, or a clinically relevant change in associated symptoms. The determination of whether there has been a significant change will be at the discretion of the Investigator; this may be in consultation with the Study Physician if there is any uncertainty.

References

FDA Guidance for Industry (issued July 2009) ‘Drug-induced liver injury: Premarketing clinical evaluation’

5.	INTERIM ANALYSES (NOT APPLICABLE).....	25
6.	CHANGES OF ANALYSIS FROM PROTOCOL	25
7.	REFERENCES	26
8.	APPENDIX (NOT APPLICABLE).....	26

LIST OF ABBREVIATIONS

Abbreviation or special term	Explanation
AE	Adverse event
AUC	Area under the concentration-time curve
AUC _{ss}	Area under the concentration-time curve at steady state
BM	Brain metastases
BMI	Body mass index
BP	Blood pressure
CSR	Clinical Study Report
¹¹ C	Carbon-eleven
C _{max}	Maximum concentration after single dose
C _{ssmax}	Maximum concentration at steady state
CAP	Continued access phase
CNS	Central nervous system
CRF	Case report form (paper)
CSF	Cerebrospinal fluid
CSP	Clinical Study Protocol
ctDNA	Circulating tumour DNA
CT	Computed tomography
CTCAE	Common Terminology Criteria for Adverse Events
DNA	Deoxyribonucleic acid
ECG	Electrocardiogram
ECHO	Echocardiogram
EGFR	Epidermal growth factor receptor
FSH	Follicle-stimulating hormone
GCV	Geometric coefficient of variation
IP	Investigational Product
K _{p_{u,u}}	Brain/plasma partition coefficient
LM	Leptomeningeal metastases
LVEF	Left ventricular ejection fraction
MedDRA	Medical Dictionary for Regulatory Activities
MRI	Magnetic resonance imaging
MUGA	Multigated acquisition angiogram
NSCLC	Non-small cell lung cancer
%ID	Percent of radioactive drug injected
PET	Positron emission tomography
PK	Pharmacokinetics
RECIST	Response Evaluation Criteria in Solid Tumours
ROI	Region of interest
RNA	Ribonucleic acid
SAE	Serious adverse event
SAP	Statistical analysis plan

Abbreviation or special term	Explanation
SD	Standard deviation
SOC	System organ class
SUV	Standardised uptake value
T_{max}	Time of maximum drug concentration after single dose
T_{SSmax}	Time of maximum drug concentration at steady state

AMENDMENT HISTORY

Date	Brief description of change
N/A	

1. STUDY DETAILS

1.1 Study objective

Primary objective

The primary objective of this study and the associated outcome measures are

Primary Objective:	Outcome Measure:
To determine the brain exposure of [¹¹ C]osimertinib in tumour region of interest (ROI) [brain metastases (BM), including leptomeningeal metastases (LM)] in patients with non-small cell lung cancer (NSCLC) after a single intravenous (IV) microdose and after single and multiple therapeutic doses of osimertinib	The percent of injected dose in the whole brain (%ID) and brain standard uptake value (SUV), to describe maximal radioactivity concentration in the brain ($C_{max, \%ID\ brain}$; $C_{max, SUV\ brain}$). The time of the maximum radioactivity concentration in the brain ($T_{max\ brain}$). The brain to plasma partition coefficient (concentration brain/plasma ratio) as area under the concentration-time curve ($K_p = AUC_{brain\ 0-90min} / AUC_{blood\ 0-90min}$). All parameters of exposure will include the tumour region, whole brain and anatomical regions.

AUC: Area under the concentration curve; C_{max} : Maximum concentration after single dose; T_{max} : Time of maximum drug concentration after single dose.

Secondary objective

The secondary objective of this study and the associated outcome measures are

Secondary Objective:	Outcome Measure:
To determine the pharmacokinetics (PK) of osimertinib and its metabolite (AZ5104) after multiple administrations of osimertinib	The following variables will be calculated where the data allow: maximum plasma concentration (C_{ssmax}), time to reach maximum plasma concentration (t_{ssmax}), area under the plasma concentration-time curve from zero to the last measurable time point (AUC_{ss}). Also, the metabolite to parent ratio of the AUC and maximum concentration after a single dose (C_{max}) will be calculated, as appropriate.

AUC: Area under the concentration curve; C_{max} : Maximum concentration after single dose

Safety objective

The safety objective of this study and the associated outcome measures are

Safety Objective:	Outcome Measure:
To examine the safety and tolerability of [¹¹ C]osimertinib IV doses and multiple oral doses of osimertinib in NSCLC patients with BM.	Assessment of AEs graded by the Common Terminology Criteria for Adverse Events (CTCAE) version 4.03, standard 12-lead ECGs, physical examination, vital signs (including blood pressure [BP], pulse) and evaluation of laboratory parameters (clinical chemistry, haematology, and urine analysis).

AE: Adverse event; BM: Brain metastases; IV: Intravenous; NSCLC: Non-small cell lung cancer.

CCI

1.2 Study design

The study design includes 2 phases, the imaging phase and the continued access phase. Using high resolution positron emission tomography (PET), this open-label study will examine brain distribution and retention of a microdose of [¹¹C]osimertinib in approximately 12 patients with epidermal growth factor receptor (EGFR) mutated NSCLC and brain metastases. The imaging data analysis will include quantification of the maximum radioactivity concentration of [¹¹C]osimertinib in the brain after injection (percent of injected dose entering the brain) and other parameters of brain exposure listed in Section 3.1.

An overall study plan is presented in Figure 1.

[figure not shown]
Full details of the assessments conducted at each visit are shown in Table 1 of the protocol.

The imaging phase of the study will include 3 single IV microdose administrations of [¹¹C]osimertinib and PET examinations on Day 1, Day 2 (or up to Day 8) and Day 29. Oral administration of osimertinib tablets (80 mg once daily) to patients will begin from the day of the second PET examination for at least 21 days before the third PET examination. The second phase, the continued access phase, will allow patients to continue to take osimertinib tablets (80 mg once daily) as a single agent depending on the agreement between the patient and the Investigator. Osimertinib administration will continue until, in the opinion of the Investigator, the patients are no longer deriving clinical benefit or the patients stop taking osimertinib for any other reason. No clinical data will be collected during this phase other than the sudden death of unknown reason, serious adverse events that may be related to osimertinib, outcomes of pregnancy and investigational product (IP) dispensing/accountability.

[figure not shown]
Patients not participating in the continued access phase or who discontinue treatment during the imaging phase will return to the clinic for follow-up assessments 30 days (± 7 days) after their last administration of osimertinib in the imaging phase. If the patient's last administration of osimertinib is in the continued access phase, the patient should be contacted 30 days after their last administration of osimertinib to follow up on any existing AEs/SAEs and monitor for new AEs/SAEs that may be related to the IP, and record any sudden deaths of unknown cause.

Figure 1 Overall study plan

A: Study flow

[figure not shown]

B: Study period (drug administration and imaging measurements)

[figure not shown]

C. PET examination flow

PET1

PET2 and PET3

● = Tablet dosing CT: Computed tomography; IV: Intravenous; MRI: Magnetic resonance imaging; PET: Positron emission tomography

1.3 Number of subjects

Given that this a PET study, sample size is based on the generally applied numbers in the exploratory pilot type studies, where 8 subjects is the accepted minimum number. These types of studies have no statistics to give better ground for sample size calculations. Therefore, the minimum sample size is accepted both by regulatory and scientific communities. Given the nature, no formal statistical analysis will be performed in this study. The statistical analysis will be descriptive.

The number of patients is based on the desire to obtain evaluable data while exposing as few evaluable patients as possible to the study procedures. Approximately 12 patients with NSCLC will receive osimertinib to obtain at least 8 patients to complete all study assessment procedures, and hence, evaluable for analysis.

2. ANALYSIS SETS

2.1 Definition of analysis sets

There will be 4 analysis sets considered in this study:

- The *safety analysis set* will include all patients who receive at least 1 administration of [¹¹C]osimertinib and/or osimertinib
- The *PET analysis set* will include all patients who complete at least 1 PET examination for the evaluation of [¹¹C]osimertinib brain distribution.
- The *complete PET analysis set* will include all patients who complete all three PET examinations. This analysis set is a subset of the PET analysis set and will be used in the assessment of potential treatment effects on brain metastases
- The *PK analysis set* will include all patients who received at least 1 administration of either [¹¹C]osimertinib and/or osimertinib and had post administration PK assessments of osimertinib and/or its metabolite (AZ5104) without any CSP deviations or dosing deviations that might have affected the PK analysis.

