Osimertinib 40 mg and 80 mg film-coated oral tablets, manufactured by AstraZeneca will be provided for the study. Osimertinib 40 mg film-coated tablets will be provided to be used only in the case where dose reduction is necessary.

[¹¹C]osimertinib

The radiolabelled [¹¹C]osimertinib will be manufactured *ex tempore* by the positron emission tomography centre, Radiochemistry Laboratory at the Karolinska Institutet, PPD [REDACTED], Solna, Sweden, from a precursor "AZ13774738" supplied by PharmaSynth AS (Tartu, Estonia) and close in time to each positron emission tomography measurement. After synthesis, the [¹¹C]osimertinib will be dissolved in a sterile buffer solution and sterile filtered and the final product will undergo quality control prior to release for human administration.

Statistical methods

All patients who receive at least 1 administration of either [¹¹C]osimertinib or osimertinib will be included in the assessment of imaging and safety. Pharmacokinetic parameters will be

Clinical Study Protocol

Drug Substance [^{11}C]osimertinib, osimertinib

Study Code D5160C00043

Version 2.0

Date 24 September 2019

summarised for all patients who had post-administration pharmacokinetic assessments without any Clinical Study Protocol deviations or dosing deviations that might have affected the pharmacokinetic analysis. Given the exploratory nature, no formal statistical analysis will be performed in this study. The statistical analysis will be descriptive. Demographic and baseline characteristics, imaging outcomes, safety outcomes, and treatment duration will be summarised using descriptive statistics, as appropriate.

TABLE OF CONTENTS

	PAGE
TITLE PAGE.....	1
VERSION HISTORY	2
CLINICAL STUDY PROTOCOL SYNOPSIS	4
TABLE OF CONTENTS	8
1. INTRODUCTION	16
1.1 Background and rationale for conducting this study	16
1.1.1 Non-small cell lung cancer and EGFR	16
1.1.2 NSCLC and brain metastases.....	17
1.1.3 [¹¹ C]Osimertinib	17
1.1.4 Osimertinib	18
1.2 Rationale for study design, doses and control groups.....	18
1.3 Benefit/risk and ethical assessment.....	19
1.3.1 Risks from study examinations (PET and magnetic resonance imaging).....	20
1.4 Study design.....	21
1.5 Study governance and oversight	24
2. STUDY OBJECTIVES.....	24
2.1 Primary objective	24
2.2 Secondary objectives	24
2.3 Safety objectives	25
CCI	CCI
3. PATIENT SELECTION, ENROLMENT, RANDOMISATION, RESTRICTIONS, DISCONTINUATION AND WITHDRAWAL.....	26
3.1 Inclusion criteria	26

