8.3 Definitions of analysis sets

8.3.1 PET analysis set

All patients who complete at least 2 PET examinations will be included in PET data analysis and evaluation of [^{11}C]osimertinib brain distribution. Patients who have completed all PET examinations; will be included in the assessment of potential treatment effects.

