3. PRIMARY AND SECONDARY VARIABLES

3.1 Parameters of brain exposure of [¹¹C]osimertinib

The primary outcome variables describe the distribution of [¹¹C]osimertinib in the whole brain using a set of exposure parameters including:

- $C_{max, \%ID\ brain}$ Maximum radioactivity concentration in brain (%), expressed as the percentage of injected radioactivity (calculated as the radioactivity concentration in the region of interest multiplied with the volume of the region of interest), divided by the radioactivity injected, and multiplied by 100
- $C_{max,SUV\ brain}$ Maximum radioactivity concentration in brain, expressed as the standardized uptake value corresponding to the regional radioactivity concentration normalized for injected radioactivity and body weight
- $T_{max\ brain}$ Time of maximum radioactivity concentration in the brain (min), obtained directly from the observed concentration versus time data
- $AUC_{brain\ 0-90}$ Area under the brain radioactivity concentration-time curve between 0 and 90 minutes (SUV*min) after injection calculated by the linear trapezoidal rule
- $AUC_{blood\ 0-90}$ Area under the plasma radioactivity concentration-time curve between 0 and 90 minutes (SUV*min) after injection calculated by the linear trapezoidal rule
- K_p Brain plasma partition coefficient – ratio of radiolabelled drug in brain to that in plasma calculated as $AUC_{brain\ 0-90}/AUC_{blood\ 0-90}$
- V_T Total distribution volume (ml/cc) quantified using kinetic compartment model

Radioactivity concentrations (as %ID) for the whole brain, tumour regions and anatomical regions will be plotted as time activity curves for individual subjects as well as an overlain plot for all subjects with arithmetic mean curve. These figures along with PET images after administration of [¹¹C]osimertinib will be prepared by the AZ PET Centre at Karolinska Institutet.

Exposure parameters will be summarised for all subjects in the PET analysis set using descriptive statistics. Geometric mean and geometric CV% will not be calculated for T_{max} brain. A by-subject appendix of individual exposure parameters will be provided.

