4.3 Analysis methods

4.3.1 Screening and demographic measurements

Disposition of patients

A summary table will be presented specifying the number of patients enrolled, who received treatment, who completed the study, and who terminated prematurely. Data will be summarised across all patients.

In addition, the number of patients included in safety analysis set as well as important protocol deviations will also be summarised within separate tables. These data will be summarised across all patients.

Demographic data

Descriptive statistics will be presented for age, height, weight and BMI. In addition, frequencies and percentage of patients will be tabulated for the categorical variables age group (< 40, >=40 up to 50, >=50 up to 65, and >=65 years), smoking status (never, former, and current), sex and ethnic group. Data will be summarised across all patients.

Concomitant medication

Prior medications, concomitant and post-treatment medications are defined based on imputed start and stop dates as follow:

- Prior medications are those taken prior to study treatment with a stop date prior to the date of first IV microdose administration of [¹¹C]osimertinib
- Concomitant medications are those with a stop date on or after the date of first IV microdose administration of [¹¹C]osimertinib (and could have started prior to or during treatment)
- Post-treatment medications are those with a start date after the date of last IV microdose administration of [¹¹C]osimertinib or oral osimertinib, whichever is later

Concomitant medications will be summarised by the coded terms in separate tables per whether the medication is allowed or disallowed based on Appendix C of the clinical study protocol. For inclusion in concomitant medication summaries, incomplete medication start and stop dates will be imputed as detailed in Section 4.2.3.1. The number of patients receiving a medication will be summarised across all patients. A patient is only counted once even if they receive the medication more than once. For detailed information regarding concomitant treatments see Section 7.7 of the protocol.

Other baseline data

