6. CHANGES OF ANALYSIS FROM PROTOCOL

There are no changes in analyses.

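### The PET analysis set needs two scans in the protocol but one in the SAP with no change recorded; the target of 8 names two different groups; and brain-metastasis effects are tied to PET completion

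*SAP*

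**What the plan says.** **PET analysis set.** Protocol 8.3.1: "All patients who complete at least 2 PET examinations will be included in PET data analysis". SAP 2.1: the set "will include all patients who complete at least 1 PET examination for the evaluation of" tracer distribution. SAP 3.1 puts the primary variables on it: "Exposure parameters will be summarised for all subjects in the PET analysis set using descriptive statistics". SAP section 6: "There are no changes in analyses". The protocol synopsis (Statistical methods) is looser again: patients given at least one administration of tracer or "osimertinib will be included in the assessment of imaging and safety". For disposition, SAP 4.3.1 says "the number of patients included in safety analysis set as well as important protocol deviations will also be summarised within separate tables"; it mentions no count for either PET set.

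**The target of 8.** Protocol 1.4 calls a patient evaluable with at least two PETs, one on the microdose alone and one with oral drug, and enrols about 12 to obtain 8 such patients. The synopsis and protocol 8.2 attach the 8 to patients who finish every study procedure. SAP 1.3 does the same and says that those patients are evaluable as a consequence.

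**Treatment effects.** Protocol 8.3.1, second sentence: "Patients who have completed all PET examinations; will be included in the assessment of potential treatment effects". SAP 2.1, on the three-scan subset: it "will be used in the assessment of potential treatment effects on brain metastases". Protocol 8.5.4 and SAP 3.4 take brain-metastasis response from brain MRI by CNS RECIST, and their visible text names no analysis set. Table 1 footnote e lets MRI-2 fall on a different day from PET3, within 7 days.

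**The concern.** The study is descriptive, so no error rate or power is at stake. What the report offers is a set of summaries, and each one depends on who is counted.

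1. The n behind the PET1 exposure summary depends on which document is followed, while SAP section 6 tells the reader that both give the same answer. The planned disposition tables would not show the difference.
2. PET3 is the only scan after multiple dosing. The multiple-dose part of the primary objective and hypothesis 2 (protocol 1.2) need it. Under protocol 1.4 a patient with PET1 and PET2 counts towards the 8 without contributing to either.
3. Change in size and number of brain metastases at 3 weeks is a stated purpose (protocol 1.1.3 and hypothesis 3). If these effects are assessed only in patients with three PETs, someone with a baseline and a follow-up MRI can be lost for a reason that has nothing to do with the MRI.

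**Working it through.** **The plan's own figure.** The documents give about 12 enrolled to obtain 8, with no formula and no dropout rate. The implied attrition is 1 − 8/12 = 33%, and 8/(1 − 1/3) = 12. This is consistent but circular. No stated number is wrong. All completion rates and responder counts below are assumptions; 12, 8 and the SD of 0.42 are from the documents.

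**1. Who is in the PET set**

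| Patient has | Protocol 8.3.1 | SAP 2.1 |
|---|---|---|
| PET1 only | out | in |
| any two PETs | in | in |
| all three PETs | in | in |

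Let d be the share of patients with PET1 only. The expected number affected is 12d, and the chance of at least one is 1 − (1 − d)^12.

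| d | Expected | P(at least one) |
|---|---|---|
| 5% | 0.6 | 0.46 |
| 10% | 1.2 | 0.72 |
| 20% | 2.4 | 0.93 |

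Effect on a mean: adding one patient who lies k SD from the mean of 8 others moves it by k × SD/9. As a stand-in SD take 0.42 %ID, from the three monkeys in protocol 1.1.3. Then k = 1 gives 0.42/9 = 0.047 and k = 2 gives 0.84/9 = 0.093 %ID.

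**2. Whether 8 is reached**

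Let p be the share with the two scans that protocol 1.4 asks for, and m the share of those who lack the remaining scan. Three-scan patients have probability p(1 − m). With X binomial on 12, compare P(X ≥ 8) under each reading.

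| p | m | Two scans | Three scans | Difference |
|---|---|---|---|---|
| 0.95 | 10% | 1.000 | 0.979 | 0.02 |
| 0.95 | 20% | 1.000 | 0.862 | 0.14 |
| 0.90 | 10% | 0.996 | 0.940 | 0.06 |
| 0.90 | 20% | 0.996 | 0.775 | 0.22 |
| 0.80 | 10% | 0.927 | 0.775 | 0.15 |
| 0.80 | 20% | 0.927 | 0.554 | 0.37 |

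Three-scan patients are a subset of two-scan patients, so each difference is the probability that the two readings disagree on whether 8 was reached. It is a lower bound against the all-procedures wording, which also covers MRI, CT and CSF. The remaining scan may be PET2 rather than PET3, so these figures are not the chance of a PET3 shortfall.

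A near-absence of three-scan patients is improbable. At the lowest rate used, 0.80 × 0.80 = 0.64, the chance that 3 or fewer of 12 have all three scans is 0.007.

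**3. A patient with both MRIs and no PET3**

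Suppose 8 three-PET completers with 6 responders: 6/8 = 75% (exact 95% CI 35 to 97%). Keeping one further patient who has both MRIs gives 6/9 = 67% (30 to 93%) if that patient does not respond, or 7/9 = 78% (40 to 97%) if the patient does. The estimate moves by 3 to 8 percentage points, far inside its own interval.

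**The case against.** **On the PET set.** The SAP's set is the wider one, so following it loses nothing. SAP 3.1 gives a by-subject appendix and SAP 4.1 requires n in every summary, so a careful reader could recover the difference. This stands, and it is why the effect is small. It does not make SAP section 6 correct. The synopsis wording adds little to the conflict: it names no PET set, and a patient with no scan supplies no PET value.

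**On the 8.** SAP 1.3 can be read as a sufficient condition: anyone who completes everything certainly has the two scans in protocol 1.4. On that reading SAP 1.3 does not redefine the term, and what remains is which group the number 8 counts. A reader might infer that the study could report success with hardly any PET3 data. Protocol 1.4 permits that on paper, but under the rates above it is very unlikely, and no stopping or success rule depends on reaching 8.

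**On treatment effects.** Neither set definition mentions MRI; the link is an inference from the visible read-out. Text is redacted in SAP 3.4, protocol 1.4, Table 1 footnote h and after the safety objectives in both documents, and a set for the MRI outcomes may be named there. The three-PET set also has a proper use in hypothesis 4, which relates change in metastases to regional exposure. Footnote t reschedules PETs that are missed or fail technically. SAP 4.1 already shows N beside n for categorical outcomes. All of this stands and limits the point.

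A reader might go further and say that the completer rule inflates response by half, for example 6/8 = 75% against 6/12 = 50%. The documents do not support that. The ratio is 8/12 whatever the number of responders, so it shows no bias. Most patients who leave the imaging phase early would have no MRI-2 under any set, since continued access collects no clinical data of that kind (protocol 4.3). That is missing data, and the set definition did not cause it.

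**Conclusion.** The conflict over the PET analysis set is certain: two scans in protocol 8.3.1, one in SAP 2.1, on the set that carries the primary exposure summaries, with no change declared. It is likely to touch at least one patient if a tenth or more stop after PET1, and it should move a mean very little. That size rests on an assumed PET1-only rate and an SD from three animals.

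The target of 8 is ambiguous, chiefly within the protocol itself (section 1.4 against the synopsis and 8.2). Under the rates tried, the two readings disagree on whether it was met with probability of at least 0.02 to 0.37. The consequence is confined to what the report may claim about multiple-dose exposure.

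The restriction on treatment effects is shared by both documents and is not a conflict between them. As far as the visible text goes, it removes a patient with both MRIs and no PET3. That should be uncommon, the numerical effect is small, and confidence is moderate because of the redactions. The three points together merit correction because the remedy costs almost nothing. They do not threaten the study's conclusions.

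**What to change.** 1. Use one minimum for the PET set in protocol 8.3.1 and SAP 2.1 (at least one PET keeps all data), bring the synopsis into line, and record the change in SAP section 6. Add counts for the PET and complete PET sets to the disposition tables in SAP 4.3.1.
2. State which group the 8 refers to, use it in the synopsis, protocol 1.4 and 8.2 and SAP 1.3, and report how many patients have PET3. Enrolment stays at about 12.
3. In protocol 8.3.1 (second sentence) and SAP 2.1 and 3.4, summarise CNS RECIST response and change in size and number of metastases in all orally dosed patients with a baseline and a follow-up brain MRI, whether or not PET3 was done. Show beside it the number of dosed patients without MRI-2. A percentage of all dosed patients is an optional addition. Keep the complete PET set for analyses that use PET3, such as the correlation in hypothesis 4. If a redacted passage already names a set for the MRI outcomes, cross-refer to it.

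The cost is wording at the next amendment and a few table rows, with no extra patients, scans or visits. The response result may look slightly less favourable.
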